6.1.1 Clinician Administered Dissociative Symptom Scale (CADSS-6; Rodrigues, 2021)

The CADSS-6 is a shorter form developed for easier clinical use of the 23-item CADSS (Bremner, 1998). There are 5 options for each question: 0=not at all; 1=Mild; 2=Moderate; 3=Severe; 4=Extreme. The 6 questions are presented in 3 areas:

1. Derealization
2. Depersonalization
3. Amnesia

6.1.2 The Quick Inventory of Depressive Symptomatology (QIDS-SR 16; Rush, 2000, Rush, 2003)

The QIDS-SR 16 is derived from the 30-item Inventory of Depressive Symptomatology (IDS). This self-report version will be utilized in the study. It has 16 items that assess nine DSM-IV diagnostic symptom domains: sad mood, poor concentration, self-criticism, suicidal ideation, anhedonia, energy/fatigue, sleep disturbance, decrease/increase in appetite/weight, and psychomotor agitation/retardation.

6.1.3 Psychedelic Music Questionnaire Short Form (PMQ-SF; Douglas Mental Health University Institute, 2021)

The PMQ-SF assess the impact of music on patients receive Ketamine for treatment resistant depression. It looks at measures of mood, anxiety, suicidality and psychological/physical pain through the rating of 15 statements and then 2 free answer questions. Music is believed to improve Ketamine tolerability.

6.2 Wavepaths Music Tract

A music track will be played during the sessions only for individuals in this research study. This music track is from Wavepaths Ltd and will be started after the baseline EEG measurements are taken but prior to the Ketamine administration. The music played is very uniform in tone throughout the session but there is no repetition in the tract. It will be played with dedicated speakers in the session room.

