There are inter-individual genetic variations to psychedelic drug effects. Testing for specific genetic markers helps determine the effects expected. This study will look at the following five genetic markers:

- HTR2A
- CYP2B6 gene
- C4A and C4B genes
- NRG1 gene
- DISC1 gene

This observational study will observe genetic markers and EEG patterns from pre, during and post Ketamine administration.

2. Objectives and Purpose

The objective of this observational study is to determine the effects of routine, intramuscular, clinically administered Ketamine on the brain's electrical activity and biomarkers. The brain activity will be measured with an EEG electrode cap and the biomarkers will be collected via a cheek swab.

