2.2 Secondary Objectives

The secondary objectives are to:

- Evaluate neurological changes during Ketamine sessions via EEG
- Evaluate persistent neurological changes in a follow up session post-treatment
- Identify biomarkers based on neurological changes during Ketamine sessions via cheek swab

3. Study Description

This is an Open Label Observational Study with the primary objective to assess brain activity in patients prior to, during and after Ketamine treatment and to assess genetic markers prior to Ketamine treatment. This is a non-interventional study that will observe the EEG pattern of participants who, per standard of care, are treated with intramuscular Ketamine. The administration of the Ketamine during this study is not considered investigational. The experimental intervention, measurements via EEG, will be offered to patients of the study

site presenting for intramuscular (IM) ketamine treatment per the site's established and evidence-based protocol as part of their regular clinical care. Participants in this study have already been determined to have a medically appropriate indication for IM Ketamine treatment, independent of enrollment in this study. Given the requirement, per study protocol, to wear an EEG headset, permit a video recording of the session and complete study measures, participants will be compensated by having treatment costs paid by the study sponsor.

There will be 36 participants enrolled.

4. Scheduling of Visits

All visits will occur at the clinic of the principal site investigator. The study will enrol for approximately 3-4 months. All times should be recorded using the 24-hour clock.

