5.1 Inclusion Criteria

1. Primary DSM-V diagnosis of treatment-resistant Major Depressive Disorder (may have secondary diagnoses of general anxiety, substance disorder)
 - Non-responders to at least 2 previous anti-depressant medications prescribed by a physician in the past five years
 - Score of ≥ 20 on Montgomery-Asberg Depression Rating Scale (MADRS) (i.e., moderate to severe depression)
2. All genders aged 21 to 60 years of age
3. Prescribed Ketamine or currently being treated with Ketamine for treatment-resistant Major Depressive Disorder
4. Willing to wear an EEG headset and an eye mask
5. Willing to permit a digital video recording to be collected for safety monitoring
6. Willing to listen to ambient sound
7. Willing to have a genetic cheek swab

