10.1 Sample Size Considerations

The objective of the study is to assess baseline brain activity and genetic markers and secondarily to measure neurological changes during Ketamine sessions. This is an open-label, observational study to determine the feasibility of these measurements. The intent is to enrol 36 participants which should have the precision needed to observe and compare EEG activity pre, during and post Ketamine administration.

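### Study-only music starts between the resting EEG and the injection, so a resting-versus-in-session EEG contrast measures Ketamine given with study music, not routine Ketamine

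*Combined protocol and SAP*

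**What the plan says.** Section 6.2 states: "A music track will be played during the sessions only for individuals in this research study". The track "will be started after the baseline EEG measurements are taken but prior to the Ketamine administration". Section 7 repeats that order, and the visit lists in 6.4 to 6.6 follow it: resting EEG (5 ± 2 minutes eyes closed, 5 ± 2 minutes eyes open), then music, then injection. The schedule in section 6 marks music at every Ketamine visit, V2 to V11.

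The same schedule has a separate row for a continuous recording that begins before the injection and ends 15 minutes after the session. No length is given for any part of it that falls after the music starts and before the injection.

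The eye mask appears once, in inclusion criterion 4: "Willing to wear an EEG headset and an eye mask". Nothing says when it goes on or comes off.

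The stated purpose in section 2 is to "determine the effects of routine, intramuscular, clinically administered Ketamine on the brain's electrical activity and biomarkers". The first secondary objective is to "Evaluate neurological changes during Ketamine sessions via EEG". Section 10.1 justifies 36 participants by the need to "observe and compare EEG activity pre, during and post Ketamine administration". Section 10.2 plans descriptive summaries only, with no analysis windows and no handling of music.

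**The concern.** The defined resting reference is taken with the study track off, and all on-drug EEG follows the start of the track. Two things change between reference and comparison, and the plan names only one of them as the cause. Any EEG response to sustained sound would be reported as part of the Ketamine effect.

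The track is not part of routine care, so the result would not describe routine Ketamine even if it were perfectly precise. Nor does the protocol treat music as inert: section 6.1.3 says it is thought to help patients tolerate Ketamine, and a questionnaire on its impact is included. At stake are the interpretation of the in-session secondary objective, the section 2 purpose, and any phenotype correlation in section 10.3 that is built on in-session change.

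**Working it through.** **Plan's own figure.** The 36 participants in section 10.1 cannot be reproduced: no error rate, power, effect size, SD, interval width or dropout is given. The point does not depend on that number.

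**Identifiability.** Let μ be the resting level, M the shift due to music and K the shift due to Ketamine, taken as additive for now.

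| EEG window | Music | Ketamine | Expected value |
|---|---|---|---|
| Resting, pre-injection | off | off | μ |
| In session | on | on | μ + M + K |

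In-session minus resting = M + K. The design matrix has rank 2 for 3 parameters. Stacking 10 sessions repeats the same two rows, so the rank stays at 2. Across 36 × 10 = 360 planned sessions, K is not separable from M in this contrast.

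**With a music-on, pre-injection window.** Its expected value is μ + M, the rank rises to 3, and in-session minus this window = K. If music and Ketamine interact by an amount I, the difference is K + I, the Ketamine effect in the presence of the track.

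**Mask.** Let E be a mask effect.
- Mask already on in the new window: the difference is still K.
- Mask put on only after the injection: the difference is K + E, and K is not estimable.

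Hence mask timing has to be stated.

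**Does the present recording already hold such a window?** Possibly, since it starts before the injection. But the visit lists describe 75 minutes of continuous EEG, which equals the 60-minute session plus 15 minutes, so no time is visibly allotted to it, and no section names it as a reference.

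**Size, by assumption.** For one contrast per participant with n = 36:
- 95% half-width of a mean within-participant change = t(0.975, 35)/√36 = 2.030/6 = 0.34 SD.
- Suppose K = 0 and M = d SD of the within-participant change. The paired t statistic is noncentral t with 35 degrees of freedom and noncentrality d√36 = 6d. At an assumed two-sided 5% level:

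| d (assumed) | 6d | Probability of a significant contrast |
|---|---|---|
| 0.1 | 0.6 | 9% |
| 0.2 | 1.2 | 22% |
| 0.3 | 1.8 | 42% |
| 0.4 | 2.4 | 65% |
| 0.5 | 3.0 | 83% |

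The documents plan no such test and give no music effect; the table only shows how a music response could pass for a Ketamine response. More data narrow the interval around M + K, not around K.

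**Correlations.** For participant i with correlate G, in-session change is M_i + K_i, and cov(M_i + K_i, G_i) = cov(M_i, G_i) + cov(K_i, G_i). If M_i is the same for everyone, the first term is zero. A spurious association needs the correlation to use in-session change and the music response to vary with G; unrelated variation in M_i only adds noise.

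**Visit 12.** Section 6.7 lists the music start both before and after the Day 74 EEG; the schedule marks no music at that visit. Whether the Day 74 rest is music-off, like the earlier rests, cannot be told.

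**Post-session segment.** Section 6.2 ties the music to the session, while recording continues for 15 minutes afterwards. Whether those minutes have music is not stated.

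**The case against.** The case for leaving the plan alone has weight.

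- The primary objective (section 2.1) uses baseline EEG and genetic markers as predictors, and that EEG precedes the music. Pre-session rest compared across Sessions 1 to 10 is like with like. Both points stand.
- The affected objective is secondary and speaks of changes during sessions, not changes caused by Ketamine; section 10.1 describes a feasibility study. This stands for that objective, but section 2 does claim effects of routine Ketamine.
- The track is described as uniform in tone, so change over time while it plays is not a music-on versus music-off comparison. This stands for within-session trends. It does not supply a pre-drug reference.
- No section makes the resting block the sole reference. True, but none names another, and the resting block is the only pre-injection EEG with a set length.

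A reader might go further and infer that the effect of Ketamine cannot be recovered at all, that the mask certainly changes state along with the music, that the baseline is recorded in silence, or that all gene and questionnaire correlations are biased. The documents do not support these readings. The recording may hold a usable music-on, pre-injection segment; mask timing is not given; the study track is off at baseline, but silence is not stated; and a music shift common to all participants leaves correlations across participants unchanged.

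**Conclusion.** The concern holds for one contrast. As scheduled, resting versus in-session EEG estimates Ketamine plus study music at all 10 sessions for every participant, and nothing in the design separates them. The bias equals the music effect if effects add; its size is unknown, and the 9% to 83% range rests on assumed shifts of 0.1 to 0.5 SD, no Ketamine effect and an assumed 5% test.

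It affects the in-session secondary objective and the section 2 wording, and the correlations only under the conditions shown above. The mask may add to the problem. Because the primary predictor objective and the between-session resting comparisons are not affected, this should be fixed but does not undermine the study as a whole. It is best settled before data collection, since a reference window that was not recorded cannot be recovered.

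**What to change.** 1. In 6.2 and 6.4 to 6.6, set a fixed music-on, eyes-closed window of about 5 minutes before the injection, within the running EEG, with the mask in the same state as during the session. Name it as the reference for all in-session change.
2. Keep the music-off rest for between-visit comparisons. Reconcile section 6.7 with the schedule so that the Day 74 rest is recorded without music, like the earlier rests.
3. State when the mask goes on, and fix one point at which music and mask end relative to the 15-minute post-session recording.
4. Reword section 2 and the reporting of in-session results to Ketamine given with study music.

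Cost: a short amendment and about 5 more minutes per session, 360 × 5 = 1,800 minutes or about 30 hours over the planned sessions, with no new visits or equipment. Limits: drift over time within a session, and any music-Ketamine interaction, would remain. If the window is not added, item 4 is the minimum.

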6.3 Screening Visit 1 (Day 0)

Before a participant is enrolled, and prior to any evaluations, the investigator or designee must explain the study in sufficient detail to allow for an informed decision to participate. Proper participant preparation is essential for participant comfort during the Ketamine treatment and will be discussed with each participant.

Once informed consent is obtained, the following evaluations will occur:

- Demography collected
- Medical history collected
- Current medical conditions collected, along with medications
- Eligibility criteria reviewed

Once complete, the first session will be booked for the next day (± 1 day).

6.4 Visit 2 (Day 1, \pm 1 day), Session 1

The following evaluations are conducted prior to the session beginning:

- Cheek swab
-  Administration of questionnaires (CADSS-6, QIDS-SR-16, PMQ-SF)
- Administration of EEG
- EEG measurements taken prior to Ketamine administration
 - 5 ± 2 minutes with eyes closed
 - 5 ± 2 minutes with eyes open
- Start the music track

The following evaluations are conducted during and after Ketamine administration:

- Ketamine administered intramuscularly, as per the usual clinical care
- EEG measurements taken throughout 60-minute session and completed 15 ± 2 minutes after end of session (e.g., at end of 75 minutes of continuous EEG)
- Digital video recording will be collected for safety monitoring

6.5 Visit 3 to Visit 10 (Days 3, 5, 8, 11, 18, 25, 32, 46, \pm 2 days), Sessions 2 to 9

- Administration of EEG
- EEG measurements taken prior to Ketamine administration
 - 5 ± 2 minutes with eyes closed
 - 5 ± 2 minutes with eyes open
- Start the music track
- Ketamine administered intramuscularly, as per the usual clinical care
- EEG measurements taken throughout 60-minute session and completes 15 ± 2 minutes after end of session (e.g., at end of 75 minutes of continuous EEG)
- Digital video recording will be collected for safety monitoring

6.6 Visit 11 (Day 67, \pm 2 days) Session 10

- Administration of questionnaires (CADSS-6, QIDS-SR-16, PMQ-SF)
- EEG measurements taken prior to Ketamine administration
 - 5 ± 2 minutes with eyes closed
 - 5 ± 2 minutes with eyes open

- Start the music track
- Ketamine administered intramuscularly, as per the usual clinical care
- EEG measurements taken throughout 60-minute session and completes 15 ± 2 minutes after end of session (e.g., at end of 75 minutes of continuous EEG)

7.1 Packaging, Labelling and Storage

The EEG device will be stored in a locked area between uses.  device will be utilized for all participants. After each use, the device will be cleaned appropriately, as per manufacturer's instructions. Between each two recording sessions, the electrodes attached to the headset will be replaced. At the end of the study, the device will be returned to Entheon Biomedical Corp.

7.2 Administration

EEG technologists from Zeto Inc. will train the site staff on the use of the device.

8. Warnings, Precautions and Contraindications

EEG is a safe procedure that has been used for many years. The test causes no discomfort to the participant. The electrodes record brain activity but do not produce any sensation and there is minimal risk of getting an electric shock as there is no current being directly delivered to the participant. Using the gel-free version is less stressful for the participant.

9. Assessment of Safety

This is a non-interventional study. Adverse events to be reported will be those related to the administration of the EEG device, not the Ketamine as it is being used as per standard of care. Participants will be observed for the entire time of their treatment. A nurse will check in on the participant regularly to minimize adverse events from occurring. The digital video recording can be viewed from outside the room to ensure safety.

The investigator is responsible for recording and reporting all adverse events observed or reported during the study from informed consent signature until the date of completion or discontinuation.

9.1 Definitions

An Adverse Event (AE) is defined as any untoward medical occurrence in a participant during a clinical study, regardless of the causal relationship. All AEs that occur during the Ketamine administration will be collected in the study documentation. Only AEs that occur during the EEG administration will be reported in the case report forms.

A Serious Adverse Event (SAE) is defined as any untoward medical occurrence in a participant during a clinical study defined as:

- Resulting in death
- Life-threatening
- Requiring inpatient hospitalization or prolongation of existing hospitalization
- Resulting in permanent or significant disability/incapacity

- Resulting in congenital anomaly/birth defect

All SAEs will be reported by the investigator to the sponsor within 24 hours and to the IRB, as per their reporting guidelines. Note that SAEs are not necessarily causally associated with the study. All SAEs will be monitored by the sponsor.

10. Data Management and Study Assessments

This study is open label and observational, therefore it has inherent limitations. There is limited control over participant assessments as the treatment is per standard of care. The strength of this design is that it reflects daily clinical practice more closely than randomized controlled studies. Real-life observational data is essential to improve clinical practice worldwide.

The trained investigator staff will enter the data required by the protocol into the case report forms (CRFs) from source documents. A Clinical Research Associate (CRA) will review the CRFs and source documents for data discrepancies and issue queries. The CRA is responsible for checking the quality of data and ensuring that the investigative site is adhering to the study protocol. Source data verification is an essential part of the monitoring process, and the Investigator must grant direct access to the participant's source data.

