2.1 Primary Objective

The primary objective is to study what baseline EEG measures and genetic markers predict a Ketamine treatment response among participants with treatment-resistant Major Depressive Disorder.

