10.3 Outcome Measures

The Primary Outcome Measure is the inter and intra patient variability in neurological activity.

The Secondary Outcomes are:

1. Correlation of neurological phenotypes with genetic markers
2. Correlation of neurological phenotypes of Clinician Administered Dissociative Symptom Scale (CADSS-6).
3. Correlation of neurological phenotypes of depressed patients with Quick Inventory of Depressive Symptomatology (QIDS SR-16)

4. Correlation of neurological phenotypes Psychedelic Music Questionnaire Short Form (PMQ-SF)

11. Administrative Procedures and Ethical Considerations

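### The EEG–QIDS correlation has no stated adjustment for baseline severity, and with everyone on ketamine any association found is prognostic, not ketamine-specific

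*Combined protocol and SAP*

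**What the plan says.** Section 2.1 sets the primary objective as finding "what baseline EEG measures and genetic markers predict a Ketamine treatment response". Section 3 words it differently: "This is an Open Label Observational Study with the primary objective to assess brain activity in patients prior to, during and after Ketamine treatment". Section 10.3 then gives a third version: "The Primary Outcome Measure is the inter and intra patient variability in neurological activity". Response is not defined anywhere. All participants receive intramuscular ketamine as standard care, and no comparison group is described. Section 10 opens with a general caveat, "This study is open label and observational, therefore it has inherent limitations", and goes no further on this point.

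The depression score enters the analysis once, as secondary outcome 3 in section 10.3: "Correlation of neurological phenotypes of depressed patients with Quick Inventory of Depressive Symptomatology (QIDS SR-16". The entry does not say whether the score is Session 1, Day 67, Day 74 or a change, and it names no covariate. Genes appear in secondary outcome 1, "Correlation of neurological phenotypes with genetic markers", which ties them to EEG and not to QIDS. Section 10.2 lists summary statistics only.

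Three further passages matter:

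- **QIDS timing.** Footnote 2 of the visit schedule in section 6 has QIDS-SR-16 at the first session, the last session (Day 67) and Day 74, three times in all. Section 6.1 says two occasions.
- **Entry severity.** Section 5.1 requires "Score of ≥ 20 on Montgomery-Asberg Depression Rating Scale (MADRS", so the threshold is on MADRS and not on QIDS.
- **Ketamine status.** Inclusion criterion 3 admits patients who are already receiving ketamine. Exclusion criterion 6 rules out only exposure outside the study site.

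**The concern.** Baseline EEG and the first QIDS are taken at the same visit, so an EEG feature may well track how depressed the participant is that day. Baseline QIDS in turn is related to later QIDS and to change in QIDS. A feature that carries nothing beyond current severity would then correlate with the outcome and could be reported as a predictor. The sign would depend on the score chosen. A feature that is high in severe patients looks favourable against change, because severe patients have more room to fall, and unfavourable against the final score.

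A second issue needs no calculation. When everyone is treated, an association with outcome cannot be separated from natural course or general prognosis. Wording about predicting response to ketamine claims more than the design can show. Section 1.1 says the data will feed the design of future studies, so a severity marker mistaken for a treatment predictor would be carried forward.

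**Working it through.** **The plan's own figure.** The only figure is n = 36 (section 10.1). It cannot be reproduced, because no effect size, standard deviation, interval width, alpha, power or dropout is given.

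**Inputs.** n = 36, all assumed to complete. Two quantities are not in the documents and are assumed: r, the correlation of the feature with Session 1 QIDS, and ρ, the correlation of Session 1 with Day 67 QIDS. The main range is 0.3 to 0.5 for each.

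**Step 1: size of the spurious correlation.** Let the feature relate to outcome only through baseline QIDS, with equal standard deviations at both times. Then

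- correlation with change = −r√((1−ρ)/2)
- correlation with Day 67 score = rρ

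For r = 0.4, ρ = 0.5: −0.4 × √0.25 = −0.20, and 0.4 × 0.5 = +0.20.

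**Step 2: how often a nominal two-sided 5% test rejects.** Simulation of 40,000 trials, n = 36. Adjusted means the partial correlation given Session 1 QIDS.

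| r | ρ | corr. with change | corr. with Day 67 | reject, change | reject, Day 67 | reject, adjusted |
|---|---|---|---|---|---|---|
| 0 | 0.5 | 0 | 0 | 5.0% | 4.9% | 4.9% |
| 0.3 | 0.3 | −0.177 | 0.09 | 18.3% | 8.1% | 4.9% |
| 0.3 | 0.5 | −0.15 | 0.15 | 14.4% | 14.2% | 5.0% |
| 0.4 | 0.5 | −0.20 | 0.20 | 21.3% | 21.8% | 5.1% |
| 0.5 | 0.3 | −0.296 | 0.15 | 42.6% | 14.2% | 4.8% |
| 0.5 | 0.5 | −0.25 | 0.25 | 31.9% | 31.8% | 4.9% |

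Check by Fisher z for a correlation of 0.20: atanh(0.20) × √33 = 0.203 × 5.745 = 1.165, and Φ(1.165 − 1.96) ≈ 21%, which agrees. Over the wider range r = 0.2 to 0.5 and ρ = 0.3 to 0.7, rejection is 7.3–43% for change and 6.5–57% for the final score. At r = 0 the raw tests stay at 4.9–5.2% for every ρ tried.

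**Step 3: does adjustment always repair this?** No. Suppose the feature tracks true, stable severity (correlation 0.3 to 0.5, assumed) and each QIDS score is that severity plus error (reliability 0.5 to 0.85, assumed). The adjusted test then rejects 7–25%, the raw change correlation about 5%, and the raw final-score correlation 24–83%.

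**Step 4: price of adjustment.** The correlation detectable with 80% power is tanh((1.96 + 0.84)/√33) = 0.452 unadjusted and tanh((1.96 + 0.84)/√32) = 0.458 with one covariate. For the precision of the slope, the equivalent sample size relative to the unadjusted model is approximately 36 × (1−r²ρ²)(1−r²)/(1−ρ²). At r = 0.5, ρ = 0.3 this is 36 × 0.9775 × 0.75/0.91 = 29. Simulation of the four corners of the main range gives 34, 41, 28 and 32, so adjustment loses some precision in three of the four.

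**The case against.** The best defence is that the plan does not state the analysis being criticised. Secondary outcome 3 names no QIDS score and uses neither the word raw nor the word unadjusted. If EEG were correlated with QIDS from the same visit, the mechanism would not arise. QIDS is a secondary outcome, section 10.2 is descriptive, and section 10.1 speaks of feasibility, so there is no test whose error rate could be inflated.

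Much of this stands. A reader might infer that the primary question will be answered with too many false positives. The documents do not support that: the primary outcome measure is EEG variability and no significance test is planned. A reader might also infer that genes will be falsely credited with prediction. No gene-by-QIDS analysis is listed, so for genes the gap is a missing analysis.

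A third tempting reading is that regression to the mean alone manufactures predictors. It does not: at r = 0 the rejection rate stays near 5%. The entry threshold is also on MADRS, so its effect on QIDS is indirect.

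What survives is that section 10.3 leaves an analyst free to run a plain correlation with a later or change score. A purely descriptive report would still show the spurious coefficients in the table. The general admission of limitations in section 10 does not cover this.

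**Conclusion.** The point holds in a limited form. A prediction objective is set in a single treated group, and its only planned link to depression score has no specified score and no baseline adjustment. A feature related to baseline severity can then pass as a predictor. Under the assumed main range the spurious correlation is −0.15 to −0.30 with change and 0.09 to 0.25 with Day 67 QIDS. A nominal 5% test would reject 14–43% and 8–32% of the time respectively, against about 5% adjusted.

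These sizes rest on assumed r and ρ, equal variances, complete follow-up and an error-free Session 1 QIDS taken before treatment. The last is not assured, because patients already on ketamine may enrol. It would be wrong to read adjustment as a complete cure (Step 3). It would also be wrong to expect a gain to 36/(1−ρ²), about 40 to 48 equivalent participants, since that requires a feature unrelated to baseline QIDS. In the settings where the bias arises, the figure is roughly 28 to 41.

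The interpretive part rests on no assumption: without a comparator the findings are prognostic.

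**What to change.** 1. In section 10.3, secondary outcome 3, specify a regression of Day 67 QIDS-SR-16 on the baseline EEG feature, adjusted for Session 1 QIDS-SR-16.
2. Report the unadjusted correlation with QIDS change beside it as a sensitivity analysis, because the two respond differently to measurement error. Disagreement between them calls for caution.
3. Add the same model for genotype, since the objective names genes but no analysis relates them to QIDS.
4. Record whether each participant was already on ketamine at entry, and flag or analyse those participants separately. For them Session 1 is not a pre-treatment baseline.
5. Reconcile the three administrations in the section 6 schedule with the two in section 6.1, then add Day 74 as a second outcome time.
6. Reword section 2.1 so that it asks which baseline measures *are associated with change in depressive symptoms during Ketamine treatment*, and describe results as prognostic.

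The cost is small. Session 1 QIDS is already collected, and the covariate uses one degree of freedom (detectable correlation 0.452 to 0.458). Intervals may widen when the feature is correlated with baseline QIDS, and the claim becomes softer.
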